### **10.3 Interim analyses**

In addition to the planned regular reporting to the DSMB of trial conduct and safety (see Data and Safety Monitoring Plan), formal interim analyses will be conducted for efficacy and futility on the primary trial outcome (EXAMINER score). To avoid un-blinding investigators, the analysis will be conducted by an independent data analyst/statistician; this un-blinded statistician will present the interim outcome analysis to the DSMB in a closed-session (not involving trial investigators). We will conduct the interim outcome analyses when 25% and 50% of the sample has completed their 12-month assessments. We will use an alpha spending

function approach with O'Brien-Fleming sequential boundaries to preserve the overall two-sided alpha error rate of 0.05. O'Brien-Fleming alpha levels will be 0.0051 and 0.0415 (2 analyses). If the boundary is crossed at the first interim analysis, the DSMB will convene to decide on termination or continuation of the trial based on efficacy.

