## *Sample Size and Population*

Our target sample size is 140. To achieve this sample size, **160** individuals will be enrolled to account for drop-outs. Individuals will be recruited from the greater Atlanta area to achieve a final sample of 140 (70 in candesartan group, 70 in lisinopril group). Our target population is subjects: 60 years or older, blood pressure (BP) >140/90 mm Hg or receiving antihypertensive medications, with executive MCI.

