#### Outcome Analysis

(a) Candesartan and cognitive/neuroimaging outcomes: General linear models will be used to compare the candesartan and lisinopril groups. Our main explanatory variable is the indicator for treatment group. Dependent variables will be the 12-month cognitive and neuroimaging measurements. For the cognitive analyses, our primary outcome is the executive function score derived using item response theory as outlined above in the EXAMINER methodology to account for education, age, and race influences on measures of executive abilities (developed by our collaborator, [name] team). For the cognitive outcome Mixed models with repeated measures (3 measurements) will be used. This procedure allows us to model the covariance structure to account for the potential variability across subjects in times of follow-up visits. Our main explanatory variable is the indicator for treatment group. The test of treatment effects on trial outcomes will be an interaction of treatment by visit (baseline,12 months follow-up). The main covariate adjustments will include history of prior stroke and prior exposure to ACEI/ARB. Additional covariate adjustments will be selected based on baseline statistically significant differences between the 2 randomized groups. The neuroimaging outcomes include measures of global perfusion, reactivity, FA, MD, and tractography metrics described above. **Table 3** provides a list of main variables. The multivariate models of the neuroimaging analysis will include the baseline values of the 12-month outcome variable, randomization stratification variables and other covariates that are significantly differ (at p<0.05) between the 2 groups at baseline. We will assess if the effects of randomized treatment are independent of blood pressure by comparing models with and without blood pressure change from baseline to 12 months. Summary statistics will include the model-adjusted mean and 95% confidence interval for each treatment group, and the mean (95% confidence interval) group difference on each 12-month outcome, as well as a p-value for group differences. All tests of significance on treatment group comparisons will use a two-sided alpha of 0.05.

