## 10.6 Sample Size Estimates

Using ANOVA with repeated correlated measures improves power in clinical trials. The 1 year correlation with baseline repeated measures ranged from 0.3 to 0.5 in our pilot data. The effect size for candesartan relative to lisinopril was 0.48 [mean difference 12 (pooled SD 25 sec)] for TMT-B, 0.41 [mean 5.5(13)] for cerebral blood flow and 0.24 [mean 0.30(1.2)] for vasoreactivity to CO2 in our pilot study. Using a 2-sided  $\alpha = 0.05$ , we estimate that a sample size of 140 will give us 80% power to detect at least 0.24 effect size. To account for dropout rate of 10-15% and a 55% prevalence of eligible subjects, we estimate that we need to screen 332 and enroll 160 to achieve a 140 final sample size.

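### The interim plan tests the primary outcome at 25%, 50% and the end but gives only two O'Brien-Fleming levels, which fit no such schedule; overall error is about 4.4% to 7.8% depending on the reading

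*Combined protocol and SAP*

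**What the plan says.** Section 10.3 states that "formal interim analyses will be conducted for efficacy and futility on the primary trial outcome (EXAMINER score"). The timing is explicit: "We will conduct the interim outcome analyses when 25% and 50% of the sample has completed their 12-month assessments". The method is an alpha spending "function approach with O'Brien-Fleming sequential boundaries to preserve the overall two-sided alpha error rate of 0.05". The section then gives the thresholds: "O'Brien-Fleming alpha levels will be 0.0051 and 0.0415 (2 analyses").

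It does not say which look each level belongs to, and it names no level for the final analysis. The consequence of crossing is described for one look only, with efficacy as the ground: "If the boundary is crossed at the first interim analysis, the DSMB will convene to decide on termination or continuation of the trial based on". A futility analysis is announced without any futility rule.

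Under Outcome Analysis in section 10.5, a general sentence covers the final test: "All tests of significance on treatment group comparisons will use a two-sided alpha of 0.05". No exception is made for the primary outcome. The sample size statement in section 10.6 ("we estimate that a sample size of 140 will give us 80% power to detect at least 0.24 effect size") also uses two-sided 0.05 and mentions no allowance for interim looks.

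**The concern.** Two interim looks and a final analysis need three levels, and only two are given. O'Brien-Fleming boundaries are extremely strict early and leave the final level close to 0.05. A level of 0.0051 at a quarter of the data, or 0.0415 at half, does not have that shape.

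These numbers are the only efficacy thresholds the DSMB receives, and they also bear on how the primary result is declared. The final sample is 140, so 25% is 0.25 × 140 = 35 completers. On the literal text the DSMB would be asked to consider termination at p = 0.0051 with about 35 completers. If the final test then ran at 0.05, most of the alpha would already have been spent. Two competent statisticians could apply different thresholds from the same paragraph and reach different conclusions from the same data.

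**Working it through.** **Inputs.** Overall two-sided error 0.05, looks at 25% and 50%, and levels 0.0051 and 0.0415 (all section 10.3); final comparison at 0.05 (section 10.5); final sample 140, 70 per arm (Sample Size and Population). Information is taken as proportional to 12-month completers, so t = 0.25, 0.50 and 1. No futility stopping is credited, because no futility rule is given.

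**Method.** Under the null, the test statistics Z₁, Z₂, Z₃ are standard normal with correlation √(tᵢ/tⱼ) for tᵢ < tⱼ. The classical O'Brien-Fleming boundary is z_k = C/√t_k, with C chosen so that the probability of any crossing is 0.05. The nominal level is p_k = 2[1 − Φ(z_k)]. Crossing probabilities come from recursive numerical integration; the two readings that apply both stated levels at the interims were also simulated.

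**Step 1: can the stated pair be reproduced?** It cannot, on any schedule tried.

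| Analyses at | Classical O'Brien-Fleming | Lan-DeMets O'Brien-Fleming type |
|---|---|---|
| 50, 100% | 0.0052, 0.0480 | 0.0031, 0.0490 |
| 25, 100% | 0.00009, 0.0500 | 0.00001, 0.0500 |
| 25, 50, 100% | 0.00008, 0.0052, 0.0480 | 0.000015, 0.0030, 0.0490 |
| thirds | 0.0005, 0.0141, 0.0451 | 0.0002, 0.0120, 0.0463 |
| quarters | 0.00005, 0.0042, 0.0194, 0.0429 | 0.000015, 0.0030, 0.0183, 0.0440 |

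The nearest match is one look at 50% plus a final. There 0.0051 is almost right, but the second level should be 0.0480. With 0.0051 fixed at 50%, the final level that uses exactly 0.05 is again 0.0480.

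**Step 2: the levels for the planned looks.** For t = 0.25, 0.50, 1, C = 1.9776. Then:
- 25%: z = 1.9776/√0.25 = 3.955, p = 0.000076
- 50%: z = 1.9776/√0.50 = 2.797, p = 0.0052
- 100%: z = 1.978, p = 0.0480

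If the stated levels belong to the two interims, they are too liberal by factors of 0.0051/0.000076 ≈ 67 and 0.0415/0.00516 ≈ 8.

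**Step 3: overall two-sided error by reading.**

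| Reading | Overall error |
|---|---|
| 0.0051 at 25%, 0.0415 at 50%, final 0.05 | 7.84% (simulation 7.82%) |
| 0.0051 at 25%, 0.0415 at 50%, final 0.0415 | 7.15% (simulation 7.14%) |
| 0.0051 at 25%, no second look, final 0.05 | 5.35% |
| 0.0051 at both interims, final 0.0415 | 4.69% |
| 0.0051 at 25%, final 0.0415 | 4.51% |
| 0.0051 at 50%, final 0.0415 | 4.36% |

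**Step 4: what remains on the literal reading.** The two interim levels spend 4.36% by half-way. Holding 5% overall would leave a final level of about 0.0123. For scale, take the pilot TMT-B effect of 0.48 from section 10.6 (not an EXAMINER effect) with 70 per arm. The final test alone then has 62% power at 0.0123, against 80% at 0.048. Counting rejections at the interims, overall power is about 70% for that design, against about 81% for the proper three-look boundary (normal approximation).

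**The case against.** The best defence is that 7.8% is the least favourable reading. It requires both levels to belong to the interims and the final test to run at an unadjusted 0.05. The reference to two analyses and the ascending pair may instead mean one interim and a final. In that case overall error is 4.4% to 4.5%, and the cost is only some lost power (about 79% against 81% at an effect of 0.48). The 0.05 in section 10.5 is a general sentence covering cognitive and imaging outcomes alike, and the specific commitment in section 10.3 could be held to govern the primary test. Crossing leads the DSMB to convene, not to stop automatically, and no efficacy action is stated for the 50% look.

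Much of this stands as a limit on size. The error should be reported as a range, a final test at 0.05 is an inference from section 10.5, and overall power is a fairer measure than power of the final test alone. None of it rescues the numbers. The conservative reading contradicts the two looks planned in the same paragraph, leaves one of them without a boundary, and still does not give an O'Brien-Fleming level. Nothing elsewhere in the protocol supplies the missing level.

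**Conclusion.** The concern holds. The two stated levels match neither the planned 25/50/100% schedule nor a 50/100% schedule, and the final level is undefined in section 10.3 and unadjusted in section 10.5. The promised overall error of 0.05 is therefore not assured: it is 7.8% on the literal text and as low as 4.4% if the pair is read as one interim plus the final. These figures assume information proportional to 12-month completers and no credit for futility stopping. The mismatch between the levels and the planned looks does not depend on the power figures. Because these are the thresholds for early stopping and bear on how the primary result is declared, this should be corrected before any interim analysis.

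**What to change.** In section 10.3, state the number of analyses and the level at each, for the primary EXAMINER test. Any one of these would do:
- Classical O'Brien-Fleming for three analyses: two-sided 0.00008 at 25%, 0.0052 at 50%, 0.0480 at the end.
- Lan-DeMets O'Brien-Fleming-type spending: 0.000015, 0.0030 and 0.0490 at the planned fractions, recomputed at the fractions actually observed.
- Drop the 25% efficacy look and use 0.0052 at 50% and 0.0480 at the end.

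Amend section 10.5 so that the final primary test uses the final boundary (0.048 or 0.049) and the 0.05 applies to other comparisons only. Say what crossing means at every efficacy look, not just the first. Since a futility analysis is announced, give its rule and say whether it is binding.

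The cost is wording, plus a small loss of power: at an effect of 0.48 with 70 per arm, testing at 0.048 instead of 0.05 takes power from 80.5% to 80.0%. Sample size and visits do not change.

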#### 10.4 Outcomes

Table 3 provides a list of main outcomes. Other Analyses' variables: Logical memory, digit span, DSST, WMH volume, regional brain measures

**Table 3:** Independent, primary and secondary outcomes and other variables to be used in the analyses

Independent:	Randomization Group (Candesartan vs Lisinopril)
Primary outcome:	Executive function (EXAMINER score)
Secondary Imaging outcomes:	Perfusion, CO2 VR, VMR, FA, MD, DTT t-scores, rs-fMRI
Mediators:	CIMT, stiffness, inflammatory markers, EPC
Tertiary outcomes:	memory, digit span, DSST, WMH volume, regional brain measures
Stratification variable:	Race, number of antihypertensive medications
Covariates:	Prior stroke and prior use of ACEI/ARB
Safety:	AE, SAE, incident dementia

#### 10.5 Data Analysis

The 2 groups will be compared on baseline demographics, education level, physical function (SPPB), IADL, DEX, mood (CESD), cognitive and vascular/inflammatory measures and APO-E genotype. Also, baseline WMH, perfusion, VR, lacunar infarcts, and hippocampal volumes will be compared between the 2 groups using independent t-tests, nonparametric rank-based tests, or chi-square tests as appropriate. We will compare number of AE, SAE and incident dementia in the 2 groups as part of our safety analysis using Fisher's exact test; adverse event categories will utilize MedDRA (Medical Dictionary for Regulatory Activities) coding. To assess possible bias due to selective dropout, baseline comparisons between participants who complete vs. do not complete 12-month outcome assessments will be performed. To assess if equivalent blood pressure was achieved in both groups we will compare mean SBP and DBP in both groups during the follow-up visits. In addition, % controlled (defined as SBP<140 mm Hg/90 mm Hg) will be calculated for each visit post-titration. We will compare the % control in both groups using chi-square.

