## *Interventions and Duration*

The intervention includes candesartan or lisinopril with add-on antihypertensive medications to achieve blood pressure control to below 140/90 mm Hg. The duration of the study is 1 year.

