receiving coil or conductive materials. Subjects will be screened for magnetic material before each study, per the standard of care at the MRI suite. Patients with pacemakers, aneurysm clips, metallic prostheses or shrapnel fragments are at risk at an MR environment and will be excluded from the neuroimaging portion of the study. Women of childbearing age will not be included. Earplugs or close fitting silicon padded headphones will be provided to protect from damage to the inner ear due to the loud tone produced by the MRI scanner. Subjects will be observed and monitored at all times by the operators, and can be moved out of the machine at their request. Subjects will be able to communicate through an intercom with the physician/scientist or technician at all times. In addition the MR gantry is equipped with a camera allowing continuous monitoring of the subjects from the MR control room; subjects are given a pneumatic bulb that starts off an alarm in the control room in case of emergency. All people entering the exam room where the magnet is located will be screened for magnetic material before entering the room. This will apply to subjects, experimenters, and staff.

(iii) **Incident dementia:** Although limited information is available, it is estimated that the yearly conversion rate is close to 7% in executive MCI. We will screen at each visit for any new diagnosis related to cognition (dementia, delirium, others), new medication started (cholinesterase inhibitors or memantine), or proxy/self-report of new diagnosis of dementia. The physician (PI) will review the clinical history with the study neurologist ([name]) and a consensus diagnosis will be made. We will compare the number of people who develop incident clinical dementia in both groups as part of our safety analyses.

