#### **8.4 Methods and Timing for Assessing, Recording, and Analyzing Safety Parameters**

At each encounter, standardized adverse event (AE) monitoring forms will be completed. At any point during the study period an adverse event is identified, it will be recorded in the participant research record along with the time/place of the event. The study physician will be immediately notified and the participant evaluated either by phone (if participant is not on site) or face-to-face (if participant is on site). Depending on the physician assessment, further evaluation maybe performed such as scheduling additional visits, further lab work, exam, or referral to the emergency department. Details about the safety parameters will be recorded and entered into a database. Comparisons between the 2 groups will be conducted to assess overall and between group differential safety.

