### **10.2 Randomization**

The study un-blinded biostatistician will provide oversight of randomization fidelity and blinding. To ensure equal distribution between the 2 groups on important confounders, we will use block randomization with stratification on:

- (1) race, (white, non-white).
- (2) number of antihypertensive medications (2 or less vs >2).

Randomization will occur in a 1:1 allocation. Four separate randomization lists will be prepared (race=white, medications=2 or less; race=white, medications>2; race-non-white, medications=2 or less; race=non-white, medications>2). Randomization will use a computerized random number generator (SAS, V9.3); the blocking number will not be revealed to investigators or research staff. Each randomization list will include the treatment group allocation, a unique allocation sequence number, and a blank field (to complete with subject study ID as randomization occurs). Randomization lists will be provided to the IDS Pharmacy. Only the pharmacy and the un-blinded statistician will have access to the randomization lists. As the pharmacist is notified that an individual subject is eligible for randomization to a given stratum, the pharmacist will select the appropriate randomization list, complete the subject ID, and prepare the appropriate blinded study product. The pharmacist will enter the subject ID, date of product randomization, and the unique allocation sequence number on a web-based data form. The statistician will monitor appropriateness of randomization (eligibility criteria met, correct stratum used, next allocation sequence used) in real time; incorrect randomizations will be immediately recorded as protocol deviations and reported to the principal investigator (in a blinded fashion).

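### Fisher's exact test is the only statistical method specified for safety; an effect estimate with a confidence interval should be added, because a non-significant result at this size would not exclude a doubling of incident dementia

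*Combined protocol and SAP*

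**What the plan says.** Section 8.4 gives the purpose of the safety comparison: "Comparisons between the 2 groups will be conducted to assess overall and between group differential safety". Section 10.5 gives the method: "We will compare number of AE, SAE and incident dementia in the 2 groups as part of our safety analysis using Fisher's exact test". It adds MedDRA coding for adverse event categories, but no effect measure, interval or margin.

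Section 8.2(iii) places incident dementia among the safety analyses and says that "it is estimated that the yearly conversion rate is close to 7% in executive MCI", after noting that information is limited. Table 3 also lists incident dementia only in the safety row.

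Estimates and intervals are planned elsewhere. Under Outcome Analysis (a), "Summary statistics will include the model-adjusted mean and 95% confidence interval for each treatment group", together with the group difference in means. That paragraph concerns the 12-month cognitive and imaging outcomes. Paragraph (b) plans bootstrap intervals for mediation effects. Neither reaches the safety outcomes. Paragraph (a) also states that "All tests of significance on treatment group comparisons will use a two-sided alpha of 0.05".

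On size, the synopsis aims for 70 participants per arm in the final sample, and section 10.6 enrols 160 to achieve it.

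**The concern.** The stated aim is to assess a difference in safety, but the only planned statistical output is a p-value. With few expected events, a p-value above 0.05 is compatible both with no difference and with a substantial excess in one arm, and it does not show which excesses the data leave open. Incident dementia is the clearest case: it is a serious event for this population, and its planned comparison is this test alone. If the analysis is done as written and nothing is added, readers receive counts and a p-value, with no planned statement of how large a harm remains possible in either direction.

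The wording also leaves the unit of analysis open. The number of AEs could mean events or participants. Fisher's test applies to participants classified as having or not having an event, not to event counts in which one person may contribute several.

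**Working it through.** **Inputs from the documents**
- Dementia risk about 7% per year (8.2(iii)). Since "The duration of the study is 1 year", this serves as the cumulative risk.
- "Randomization will occur in a 1:1 allocation" (10.2). 140 final gives 70 per arm; 160 enrolled gives 80 per arm.
- Two-sided alpha 0.05 (10.5, Outcome Analysis (a)), taken to apply to the safety tests too.

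**Assumptions not in the documents**
- 7% is the risk in the lower-risk arm.
- The harm of interest is a doubling, to 14%.
- Dementia status is known for all 70 to 80 per arm.

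**1. The plan's own figure.** Enrolment = 140/(1 − dropout): 140/0.90 = 156, 140/0.875 = 160, 140/0.85 = 165. The planned 160 fits the stated 10–15% dropout. The documents give no power figure for safety, so there is none to reproduce.

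**2. Expected cases at 7%.** 0.07 × 70 = 4.9 and 0.07 × 80 = 5.6 per arm.

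**3. Exact power of Fisher's test.** Power = Σ over x, y of Bin(x; n, p₁) × Bin(y; n, p₂) × 1[two-sided Fisher p ≤ 0.05], enumerating all tables.

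| True risks | 70 per arm | 80 per arm |
|---|---|---|
| 7% vs 7% (actual size) | 1.9% | 2.2% |
| 7% vs 14% (doubling) | 19.0% | 22.9% |
| 7% vs 21% (tripling) | 60% | 67% |
| 7% vs 25% | 79.9% | 85% |
| 7% vs 28% (quadrupling) | 90% | 93% |

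A doubling is missed 81% or 77% of the time. Power reaches about 80% at 25% with 70 per arm, a risk ratio of 25/7 = 3.6, and at 24% with 80 per arm (81.8%), a ratio of 24/7 = 3.4.

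**4. Sensitivity to where 7% sits.** If 7% is the average of the two arms (4.7% vs 9.3%), power for a doubling is 10% or 13%. If 7% is the higher risk and the other arm is halved (7% vs 3.5%), it is 6% or 8%.

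**5. Is Fisher's test the cause?** The normal approximation without continuity correction, with p̄ = 0.105, gives power Φ{[0.07√n − 1.96√(2 × 0.105 × 0.895)] / √(0.07 × 0.93 + 0.14 × 0.86)} = 27% at n = 70 and 30% at n = 80. It still misses about 70%. For 80% power, n = [1.96√0.188 + 0.842√0.1855]² / 0.07² ≈ 300 per arm. Sample size is the main cause.

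**6. What an interval would show.** The Newcombe limits combine the Wilson limits (l, u) of each arm: d − √[(p₁ − l₁)² + (u₂ − p₂)²] and d + √[(u₁ − p₁)² + (p₂ − l₂)²].
- 5/70 vs 5/70: Wilson limits 3.1% and 15.7% in each arm, so d = 0 ± √(4.05² + 8.51²) = ±9.4 points. Even with equal counts, an excess of 7 points, a doubling of 7%, is not excluded.
- 10/70 vs 5/70: Fisher p = 0.27; difference 7.1 points, 95% CI −3.5 to +18.0.
- 13/70 vs 5/70: Fisher p = 0.075; difference 11.4 points, 95% CI +0.2 to +22.8. Here the interval excludes zero and the p-value is not significant, so the two can support different statements.
- With 5/70 in one arm, the other must reach 14/70 before p falls below 0.05.

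**The case against.** Several stronger readings are tempting, and the documents do not support them.

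- A reader might infer that safety is judged by Fisher's test alone. It is not. Under section 8.9 the DSMB reviews AEs and SAEs tabulated by arm and may ask for further data and analyses. Section 8.2 adds laboratory and blood pressure monitoring, and screening at each visit with consensus diagnosis for dementia. This stands. It does not supply an estimate for the final between-group comparison, and the DSMB tabulation does not name incident dementia.
- A reader might infer that the plan will treat p>0.05 as equal safety. No section says so, claims power for safety or sets a safety margin. This stands too. The plan is silent on the point, and a guarding sentence is what is missing.
- A reader might blame the choice of Fisher's test. It is a conventional choice for sparse counts and, as step 5 shows, a less conservative test would do little better. The case for an interval does not depend on faulting the test.
- A reader might conclude that a null result would say almost nothing about safety. That goes too far. It carries one event at one assumed effect over to all safety outcomes, and a quadrupling of dementia would be detected about 90% of the time.
- Cognitive harm is also addressed by the EXAMINER score at baseline, 6 and 12 months, with a planned group difference and interval. That is relevant, but it does not replace a comparison of dementia diagnoses.

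Finally, per-arm counts would let a reader compute the interval. That is true, but it is not the same as pre-specifying it.

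**Conclusion.** The point holds as a limited one. Fisher's exact test is the only statistical method specified for AE, SAE and incident dementia, and no effect estimate or interval is planned, although section 8.4 aims at differential safety. With 70 to 80 per arm, a doubling of dementia from 7% to 14% would be detected only 19–23% of the time, so a non-significant result would not by itself exclude it. A risk 3.5 to 4 times higher would usually be found.

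The figures rest on the protocol's 7%, which it qualifies itself, on placing that rate in the lower-risk arm, on an assumed doubling, and on complete ascertainment. Step 4 shows that other placements of the 7% give lower power. The weakness lies in what is planned to be reported. It is not an error in the design, and nothing in the plan is invalid because of it.

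**What to change.** In section 10.5, for participants with at least one AE, participants with at least one SAE, and incident dementia, report the proportion in each arm and the risk difference (candesartan minus lisinopril) with a two-sided 95% Newcombe or exact unconditional confidence interval. Keep Fisher's p-value as a supplement. State that safety comparisons are not powered and that p>0.05 is not evidence of comparable safety. Base the differential-safety statement of section 8.4 on the interval, giving the largest excess not excluded in either direction. Defining the outcomes by participant also settles the unit of analysis.

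The cost is a few sentences and one more column in the safety tables, with no new data or participants. The downside is that the report must say openly that a sizeable excess of dementia in either arm cannot be excluded. DSMB review is unchanged.
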